## Delays

Cetuximab should be administered, if possible, on the same day of each week with no more than 3 days deviation. From there, a delay will be defined as a period of more than 10 days between 2 subsequent infusions (from the second infusion). The number of days delay will be calculated as follows:

$$[\text{date of infusion (i)} - \text{date of infusion (i-1)}] - 10 \text{ days, where } i=2,3,..I$$

If the value above is >0 days, then this will be classed as a delay. A subject may have more than one treatment delay throughout the course of treatment.

The summary of cetuximab treatment exposure table will include the following information:

- Duration of cetuximab therapy (weeks): summary statistics.
- Number of initiated cycles for cetuximab: summary statistics
- Total number of cetuximab infusions received: number of subjects with 0, 1, 2, 3, 4, 5, 6, 7, 8, 9, 10, >10 infusions
- Cumulative actual treatment dose of cetuximab (mg/m^2): summary statistics.
- Dose intensity of cetuximab (mg/m^2/week) excluding initial dose: summary statistics.
- Relative dose intensity of cetuximab (%) excluding initial dose: < 60%, 60% - < 80%, 80% - < 90%, 90% - 110%, > 110%.
- Number of subjects per minimum relative dose category (as defined Section 15.1)
- Number of subjects with at least one delayed cetuximab infusion, and maximum length of delay (no delay including 1-2 days delay, 3-8 days, 9-15 days, ≥16 days) – worst case

A listing will detail cetuximab exposure for each subject based on “Cetuximab administration” eCRF page.

In addition, batch numbers data, as recorded in “Accountability Group A” eCRF page will be listed.

## 15.2 Cisplatin Exposure

Analysis of cisplatin exposure will be based on the calculated actual dose levels (total dose administered (mg) / BSA (body surface area in m^2). For total dose administered, the actual dose administered as entered in the eCRF pages will be used. For BSA, BSA value collected on the

“BSA Determination” eCRF page will be used. The last available BSA of the subject on or prior to the day of dosing will be used.

The number of initiated cycles for cisplatin:

A cycle is considered initiated if at least one non-null dose of cisplatin was administered during this cycle.

The duration of cisplatin treatment (in weeks) during the study is defined as:

$$\text{duration of cisplatin} = \left( \frac{(\text{date of last dose of cisplatin} - \text{date of first dose of cisplatin}) + 21}{7} \right)$$

The total number of cisplatin infusions per subject is the count of the infusions with non-zero dose of cisplatin that the subject received.

The cumulative actual treatment dose (mg/m^2) of cisplatin per subject is the sum of the calculated actual dose levels of cisplatin that the subject received.

The dose intensity (mg/m^2/3 weeks) of cisplatin and the relative dose intensity (%) of cisplatin will be calculated for a 3-weekly cycle:

$$\text{dose intensity of cisplatin} = \left( \frac{\text{Cumulative dose of cisplatin from 1st infusion}}{\text{duration of cisplatin in weeks} / 3} \right)$$

The relative dose intensity (%) of cisplatin is defined as the dose intensity of cisplatin divided by 75 mg/m^2/3 weeks (the planned dose per cycle for cisplatin as assigned in the protocol).

### Delays

Cisplatin should be administered, if possible, on the same day of each cycle with no more than 3 days deviation. From there, a delay will be defined as a period of more than 24 days between 2 subsequent infusions (from the second infusion). The number of days delay will be calculated as follows:

$$[\text{date of infusion (i)} - \text{date of infusion (i-1)}] - 24 \text{ days, where } i=2,3,..I$$

If the value above is >0 days, then this will be classed as a delay. A subject may have more than one treatment delay throughout the course of treatment.

### Dose intensity by cycle

Each cycle is defined by a 3-week period. The dose intensity per cycle is defined by the sum of the total dose levels that the subject received within that time period, i.e. treatment(s) within the last 3 days of each cycle (e.g., day 19-21) are linked to the subsequent cycle as these administrations are regarded as premature start of the next cycle.

|                    |                                      |
|--------------------|--------------------------------------|
| Cycle 1 (week 1-3) | Cumulative dose from day 1 to day 18 |
|--------------------|--------------------------------------|

|                                 |   |
|---------------------------------|---|
| Cycle 2 (week 4-6)              | Cumulative dose from day 19 to day 39                 |
| Cycle 3 (week 7-9)              | Cumulative dose from day 40 to day 60                 |
| Cycle 4 (week 10-12)            | Cumulative dose from day 61 to day 81                 |
| ...                             | ...   |
| Cycle x (week $(x-1)*3+1-x*3$ ) | Cumulative dose from day $(x-1)*21-2$ to day $x*21-3$ |

The summary of cisplatin treatment exposure and compliance table will include the following information:

- Duration of cisplatin therapy (weeks): summary statistics.
- Number of initiated cycles for cisplatin: summary statistics
- Total number of cisplatin infusions received: number of subjects with infusions: 0, 1, 2, 3, 4, 5, 6, others, missing
- Cumulative actual treatment dose of cisplatin ( $\text{mg}/\text{m}^2$ ): summary statistics.
- Dose intensity of cisplatin ( $\text{mg}/\text{m}^2/3$  weeks) overall and by cycle: summary statistics.
- Relative dose intensity of cisplatin (%):  $< 60\%$ ,  $60\% - < 80\%$ ,  $80\% - < 90\%$ ,  $90\% - 110\%$ ,  $> 110\%$ .
- Number of subjects per minimum relative dose category (as defined Section 15.1)
- Number of subjects with delayed cisplatin infusions, and maximum length of delay (no delay including 1-2 days delay, 3-8 days, 9-15 days,  $\geq 16$  days)

In addition, a listing will provide detail on cisplatin exposure for each subject based on “Cisplatin administration” eCRF page.

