5.1 Overall Trial Design and Plan

This multicenter, open-label, randomized, parallel-group, phase III trial will randomize approximately 240 subjects with recurrent and/or metastatic SCCHN and involve approximately 30 trial centers in China. The overall trial design is illustrated in Figure 5.1.

Figure 5.1 **Schematic of the Trial Design** Screening **Treatment Period*** Safety Follow-up Period Survival Follow-Period up Cisplatin/Carboplatin+5-Cetuximab Safety assessment will be FU every 21 days / Max monotherapy performed 30 days (± 3 of 6 cycles Within 28 2 days) after the last dose of + Cetuximab weekly Survival status and days before trial treatment or subsequent trial immediately before starting anticancer therapy Cisplatin/Carboplatin+5treatment any new antitumor treatment FU every 21 days / Max starts of 6 cycles Safety Follow-up Eligibility Efficacy assessments End of efficacy visit every 6 weeks until PD confirmation assessment * *: This can be done after safety follow-up

5-FU: 5-fluorouracil, PD: progressive disease.

All eligible subjects will be randomized to 1 of 2 treatment arms in a 2:1 ratio:

- Arm A (cetuximab plus chemotherapy): Combination of cetuximab and cisplatin plus 5-FU. Subjects who are without progressive disease (PD) after 6 cycles of treatment will continue monotherapy with cetuximab until occurrence of PD or unacceptable toxicity.
- Arm B (chemotherapy alone): Cisplatin plus 5-FU only.

Randomization will be performed centrally using an interactive web response system (IWRS). Randomization will be stratified according to ECOG performance status (0 versus 1) and the primary tumor site (oral cavity versus hypopharynx versus others) (see Section 6.3).

Definition of treatment cycle: The ideal cycle in each arm is 21 days long and is determined by the chemotherapy as follows:

- Arm A: 1 treatment cycle consists of dosing with chemotherapy plus cetuximab on Day 1, and doses of cetuximab on Days 8 and 15, with follow-up through to Day 21 of the cycle.
- Arm B: 1 treatment cycle consists of dosing with chemotherapy staring from Day 1 of each cycle.

The regimen of cetuximab for subjects in Arm A is shown in Table 6.1. Subjects in Arm A and B will receive the same chemotherapy regimen **every 21 days**, which is based on cisplatin plus 5-FU and is shown in Table 6.4.

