Duration of treatment for subjects in Arm A: Subjects with absence of PD, as assessed by the Investigator, and unacceptable toxicity will receive a maximum of 6 cycles of chemotherapy (cisplatin plus 5-FU) and cetuximab weekly. Subjects who have not experienced PD after end of chemotherapy will continue treatment with cetuximab until either PD, as assessed by the

Investigator, or occurrence of an unacceptable toxicity. Subjects with an unacceptable toxicity due to one of the trial drugs will receive other trial drug(s) without unacceptable toxicity until either PD or completion of 6 cycles of chemotherapy. If treatment with cetuximab is delayed because of a related toxicity, the 21-day rhythm of chemotherapy is retained. A maximum of 2 consecutive cetuximab infusions can be withheld (no more than 21+3 days without cetuximab infusions) due to unacceptable toxicity, otherwise the subject must stop cetuximab. If treatment is delayed because of toxic effects of the chemotherapy, the 7-day rhythm of cetuximab infusions is retained. Chemotherapy can be delayed for a maximum of 21+3 days; after this, the subject must stop the chemotherapy treatment. The subject may continue on cetuximab monotherapy (if still benefiting).

Duration of treatment for subjects in Arm B: Subjects with absence of PD, as assessed by the Investigator, and unacceptable toxicity will receive a maximum of 6 cycles of chemotherapy. Subjects with an unacceptable toxicity due to one of the trial drugs will receive other trial drug(s) without unacceptable toxicity until either PD, as assessed by the Investigator, or completion of 6 cycles of chemotherapy. Chemotherapy can be delayed for a maximum of 21+3 days; after this, the subject must stop the chemotherapy treatment.

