6.4 Noninvestigational Medicinal Products to be Used

6.4.1 Chemotherapy

All subjects will receive chemotherapy for up to 6 cycles. As a rule, each cycle will last 21 days. In the absence of PD and unacceptable toxicity, subjects will receive 6 cycles of chemotherapy. The start of each cycle of chemotherapy will be defined by the start of cisplatin infusion (or carboplatin infusion, if cisplatin have been switched to carboplatin). Chemotherapy should be administered, if possible, on the same day of each cycle with no more than 3 days deviation.

Details of chemotherapy regimens are given in Table 6.4.

Table 6.4 Chemotherapy Regimen Every 21 Days in Arm A and B

Order of administration	Drug	Dose
First	Cisplatin infusion (refer to China package insert) on Day 1	75 mg/m ²
In the case of cisplatin intolerability ¹	Carboplatin infusion time of 15 minutes or longer, and in accordance with the China package insert on Day 1	AUC 5
Then	5-Fluorouracil Day 1 to Day 5	750 mg/m²/day continuous infusion

Abbreviation: AUC, area under serum concentration time curve.

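### SAP Section 15.2 builds by-cycle dose intensity on fixed 3-week windows that can part from the protocol's cycles, and the SAP's delay definition disagrees with its own delay categories for intervals just over the threshold

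*SAP*

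**What the plan says.** **Cycles.** Protocol Section 6.4.1 says: "The start of each cycle of chemotherapy will be defined by the start of cisplatin infusion" (or carboplatin after a switch), with at most 6 cycles. Section 5.1 treats 21 days as a target only: "The ideal cycle in each arm is 21 days long and is determined by the chemotherapy". It also says: "Chemotherapy can be delayed for a maximum of 21+3 days".

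SAP Section 15.2, under its by-cycle heading, says: "Each cycle is defined by a 3-week period". Early starts are handled by a rule that "treatment(s) within the last 3 days of each cycle (e.g., day 19-21) are linked to the subsequent cycle". The resulting table gives days 1 to 18 for Cycle 1, then "Cumulative dose from day 19 to day 39" for Cycle 2, 40 to 60 for Cycle 3, 61 to 81 for Cycle 4, and a general formula. Sections 15.3 (carboplatin) and 15.4 (5-FU) also list dose intensity by cycle, but neither gives a window rule. Section 15.1 (cetuximab) has no by-cycle dose intensity.

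**Delays.** For cisplatin and carboplatin the SAP subtracts 24 days from the interval between consecutive infusions. For cetuximab it subtracts 10. It then says: "If the value above is >0 days, then this will be classed as a delay". The summary tables report the maximum length of delay in categories that begin "no delay including 1-2 days delay, 3-8 days, 9-15 days", followed by 16 days or more. Section 15.4 lists the same delay row for 5-FU without defining a delay.

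**The concern.** A table headed by cycle will be read as what was given in each protocol cycle. Windows fixed from Day 1 match that reading only for subjects close to schedule. Once a subject has drifted far enough, the table credits a dose to a cycle in which it was not given. It can also show a cycle with no dose, a cycle with two doses, or a seventh cycle where the protocol allows six.

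The delay rows have a different problem. The 3-day tolerance is already removed by subtracting 24 (or 10), yet the first table category absorbs a further 1 to 2 days. The same interval is then a delay in one place and not in the other.

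What is at stake is the between-arm description of how chemotherapy was delivered. If delays differ between arms, so will the misattribution.

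**Working it through.** **Inputs.** Window formula: Cycle x runs from day (x−1)×21−2 to day x×21−3 (SAP 15.2). Planned start of cycle x: day (x−1)×21+1 (21-day cycles, Protocol 5.1 and 6.4.1). Full cisplatin dose: 75 mg/m² (Protocol 6.4.1.1.1). Delay length: interval − 24 for cisplatin and carboplatin, interval − 10 for cetuximab (SAP 15.1 to 15.3).

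**1. Reproduce the SAP's windows.** For x = 2, 3, 4 the formula gives 19–39, 40–60 and 61–81, as printed. For x = 1 it gives −2 to 18, shown as 1–18. Windows 5, 6 and 7 are 82–102, 103–123 and 124–144. The windows are internally consistent.

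**2. Tolerance before a dose leaves its window.**
- Late: (x×21−3) − ((x−1)×21+1) = 17 days.
- Early: ((x−1)×21+1) − ((x−1)×21−2) = 3 days.

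Assignment is therefore wrong once the cumulative shift is 18 or more days late, or 4 or more days early.

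**3. Place six infusions in the windows.**

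| Intervals (days) | Infusion days | Windows |
|---|---|---|
| 21 throughout | 1, 22, 43, 64, 85, 106 | 1, 2, 3, 4, 5, 6 |
| 24 throughout | 1, 25, 49, 73, 97, 121 | 1, 2, 3, 4, 5, 6 |
| 38, then 21s (one 17-day delay) | 1, 39, 60, 81, 102, 123 | 1, 2, 3, 4, 5, 6 |
| 42, then 21s (one 21-day delay) | 1, 43, 64, 85, 106, 127 | 1, 3, 4, 5, 6, 7 |
| 28 throughout | 1, 29, 57, 85, 113, 141 | 1, 2, 3, 5, 6, 7 |
| 26 throughout | 1, 27, 53, 79, 105, 131 | 1, 2, 3, 4, 6, 7 |
| 18, 18, then 21s | 1, 19, 37, 58, 79, 100 | 1, 2, 2, 3, 4, 5 |

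The 21-day delay lies within the limit in Protocol 5.1 and also within the 21-day limit in 6.4.1.1.4. The last row assumes that the 3-day deviation is counted from the preceding infusion. It puts 150 mg/m² in Cycle 2 and leaves five dosed windows for six infusions.

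**4. Overall dose intensity.** This uses actual first and last dose dates. For the one 21-day delay, duration = (127 − 1 + 21)/7 = 21 weeks, and dose intensity = 6×75/(21/3) = 64.29 mg/m² per 3 weeks, or 85.7% of 75. No window enters the calculation.

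**5. Delay definition against delay category (cisplatin, carboplatin).**

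| Interval | Interval − 24 | By formula | In the table |
|---|---|---|---|
| 24 | 0 | no delay | no delay |
| 25 | 1 | delay | no delay |
| 26 | 2 | delay | no delay |
| 27 | 3 | delay | 3–8 days |

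Only 25 and 26 days conflict. For cetuximab, 11 − 10 = 1 and 12 − 10 = 2, so 11 and 12 days conflict. Because the table reports the longest delay per subject, the affected subjects are those whose longest interval is one of these.

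**6. Both together.** With 26-day intervals throughout, the longest delay is 2 days, so the subject is filed under no delay. By the sixth dose the cumulative shift is 5×5 = 25 days, and the by-cycle table shows nothing in Cycle 5 and a dose in Cycle 7.

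**7. How often.** The documents give no delay rates. As an illustration only, I assumed that each of five intervals is delayed with probability 0.1 to 0.5, by a length uniform from 1 day to 7, 14 or 24 days. The share of six-cycle subjects with at least one misplaced infusion then runs from 0.1% to 77%.

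**The case against.** The strongest reply is that dose given per fixed 3-week period is a legitimate, openly stated measure of dose intensity. A subject who runs late does receive less drug per three weeks, and a rate should show that. The protocol's exposure lists (Sections 8.3.3 and 8.5.4) do not ask for by-cycle intensity at all. The quantities that matter most are computed without the windows, and subject-level listings are planned. The delay category also says openly that it includes 1 to 2 days.

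Most of this stands, and it rules out several stronger readings that a reader might infer:

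- *That skipped windows read as zero and pull the later cycle means below the dose given.* The SAP does not say whether an empty window is 0 or missing. If all intervals are at least 21 days, no 21-day window can hold two infusions. Excluding empty windows then returns 75 mg/m² in every window when every dose is 75. Any depressed mean depends on an unstated zero convention and an assumed delay distribution.
- *That every reported delay is 3 days too short.* Counting from day 24 is a disclosed definition that matches the protocol's 3-day deviation. The protocol prescribes no other way to tabulate delay length.
- *That a 5-day 5-FU infusion would be split over two cycles.* Section 15.4 gives no window rule and does not say that an infusion is apportioned.
- *That Section 15 as a whole is unsound.* The windows are written only in 15.2.

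The reply does not remove the label. A calendar window called a cycle conflicts with the protocol's definition of a cycle. Nor does it make the number of subjects flagged as delayed agree with the sum of the delay categories.

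**Conclusion.** The point holds as a limited defect in descriptive exposure tables. Following SAP 15.2 as written attributes doses to the wrong cycle for any subject whose cumulative shift reaches 18 days late or 4 days early, and the protocol's own delay allowance makes such late shifts possible. Carboplatin and 5-FU inherit the ambiguity because they are reported by cycle with no rule. The counts of initiated cycles, and of subjects on cisplatin or carboplatin by cycle, would be affected only if the same windows are used there, which the SAP does not say.

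The delay inconsistency is confined to intervals of 25 to 26 days for cisplatin and carboplatin and 11 to 12 days for cetuximab. The categories from 3 days upward follow the stated formula. For 5-FU the gap is a missing definition.

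The documents do not support a claim about how many subjects or infusions would be misplaced. Nor do they support any effect on cumulative dose, overall or relative dose intensity, minimum-dose categories, or the PFS and other efficacy analyses.

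**What to change.** 1. **Cycles.** For cisplatin, carboplatin and 5-FU, assign each dose to cycle k by the k-th actual platinum start, or the 5-FU start if platinum has been stopped. Say whether the by-cycle figure is the dose given in the cycle or a rate per 3 weeks. Use the same definition wherever initiated cycles or treatment by cycle are counted.

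   If calendar windows are kept, head the table by 3-week period, state whether an empty period counts as 0 or is excluded, and extend the rule explicitly to carboplatin and 5-FU.

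2. **Delays.** Use one threshold in the definition and the table for all four drugs. Either count any value above 0 as a delay and add a 1 to 2 day category, or keep the present categories and raise the flag to values above 2. Add a delay formula for 5-FU.

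The cost is minor SAP wording and reprogramming of descriptive exposure tables. No endpoint definition or efficacy analysis changes.

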### 15.3 Carboplatin Exposure

Analysis of carboplatin exposure will be based on the total actual dose administered. For total dose administered, the actual dose administered as entered in the eCRF pages will be used.

Number of subjects received carboplatin in each arm will be summarized.

The number of initiated cycles for carboplatin:

A cycle is considered initiated if at least one non-null dose of carboplatin was administered during this cycle.

The duration of carboplatin treatment (in weeks) during the study is defined as:

$$\text{duration of carboplatin} = \left( \frac{(\text{date of last dose of carboplatin} - \text{date of first dose of carboplatin}) + 21}{7} \right)$$

The total number of carboplatin infusions per subject is the count of the infusions with non-zero dose of carboplatin that the subject received.

The dose intensity (mg/3 weeks) of carboplatin:

$$\text{dose intensity of carboplatin} = \left( \frac{\text{Cumulative dose of carboplatin from 1st infusion}}{\text{duration of carboplatin in weeks} / 3} \right)$$

The planned dose (mg/3weeks) of carboplatin at each cycle is defined based on the Area under curve (AUC) = 5 and the Glomerular filtration rate (GFR) as collected on the “Carboplatin administration” eCRF page

$$\text{planned dose of carboplatin} = \text{AUC [mg/ml x min]} \times (\text{GFR [ml/min]} + 25[\text{ml/min}])$$

The relative dose intensity (%) of carboplatin is defined as the dose intensity of carboplatin divided by the mean of planned doses at each cycle.

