6.4.1.1.2 Carboplatin

If cisplatin results in a nonhematologic toxicity (see Section 6.4.1.2.2), carboplatin at a dose of target AUC=5 may be used as the replacement of cisplatin in subsequent cycles. The decision needs to be made in discussion with the Medical Monitor on a case-by-case basis.

Carboplatin will be administered using an intravenous infusion of 15 minutes or longer (refer to China package insert) on Day 1 of each 21-day treatment cycle. The dose of carboplatin will be calculated considering the subject's renal function as described by the glomerular filtration rate using the Calvert formula or the Chatelut formula, given that the target AUC is 5.

For those subjects in Arm A, there must be at least 1 hour between the end of the cetuximab infusion and the start of the carboplatin infusion.

Exact documentation of the actual doses, dates, and start and end times of infusions is mandatory.

6.4.1.1.3 5-Fluorouracil

Investigators should treat subjects with commercially available forms of 5-FU, and must refer to the approved 5-FU prescribing information on dosage and administration, safety issues (warnings, precautions), adverse reactions, dose reductions and omissions. Investigators should also follow their related local practice for the administration of 5-FU.

5-Fluorouracil will be administered as a dose of 750 mg/m²/day as a continuous intravenous infusion over 24 hours a day from Day 1 to Day 5 (± 6 hours of the overall duration) of each 21-day treatment cycle. Administration of 5-FU is to start upon completion of cisplatin/carboplatin administration and may be performed via the same infusion line.

For those subjects in Arm A, there must be at least 1 hour between the end of the cetuximab infusion and the start of the 5-FU infusion.

Exact documentation of the actual doses, dates, and start and end times of infusions is mandatory.

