8.5.4 Analysis of Safety

Safety analyses will be performed according to the as-treated principle. Any TEAEs will be summarized, i.e., those events that emerge during treatment having been absent pre-treatment, or worsen relative to the pre-treatment state and with onset dates occurring within the first dosing day of trial treatment until 30 days after the last dose of trial treatment. No formal statistical comparisons are planned.

The extent of exposure for cetuximab, cisplatin or carboplatin, and 5-FU will be characterized by duration (weeks), cumulative dose, dose intensity, relative dose intensity (actual dose given/planned dose), number of dose reductions, and number of dose delays.

AEs will be coded according to the current Medical Dictionary for Regulatory Affairs (MedDRA). The severity of AEs will be graded using CTCAE toxicity grades. The incidence and type of AEs, SAEs, trial treatment-related AEs and SAEs, trial treatment-related AEs by CTCAE toxicity grade, CTCAE Grade 3 and 4 AEs, trial treatment-related CTCAE Grade 3 and 4 AEs, AEs leading to death, AEs leading to discontinuation of trial treatment, will be summarized in total and for each treatment arm according to the MedDRA system organ class and MedDRA preferred terms. Missing classifications concerning trial treatment relationship will be considered as related to the trial treatment.

All deaths, deaths within 60 days after date of first dose of trial treatment and deaths within 30 days after last dose of trial treatment as well as reasons for deaths will be tabulated.

Laboratory results will be classified according to the CTCAE (version 4.03) when applicable. The worst on trial grade after date of first dose of trial treatment will be summarized. Shifts in toxicity grading from treatment start to highest grade will be displayed. Results for variables that were not part of the CTCAE (version 4.03) will be presented as below, within, and above the normal limits of the local laboratory. Only subjects with post-baseline laboratory values will be included in these analyses. The last measurement before trial treatment will serve as the baseline measurement.

Vital signs (temperature, heart rate, blood pressure, respiratory rate) will be descriptively presented.

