### Dose reductions

The minimum doses of trial drugs will be derived per subject and clustered according to the proportions of the planned dose. The minimum dose levels will be categorized as follows:

| Minimum relative dose | Cetuximab*           | Cisplatin            | 5-FU                      | Carboplatin |
|-----------------------|----------------------|----------------------|---------------------------|-------------|
|                       | (mg/m  ) | (mg/m  ) | (mg/ m  /day) |             |

| 100 % (planned dose) | 250        | 75           | 750        | AUC 5   |
|----------------------|------------|--------------|------------|---|
| ≥ 90%                | ≥225       | ≥67.5        | ≥675       | Based on
planned dose
given in the
CRF |
| ≥70 - <90%           | 175 - <225 | 52.5 - <67.5 | 525 - <675 |   |
| ≥50 - <70%           | 125 - <175 | 37.5 - <52.5 | 375 - <525 |   |
| <50%                 | <125       | <37.5        | <375       |   |

\*Initial dose will be omitted

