### Delays

Carboplatin should be administered, if possible, on the same day of each cycle with no more than 3 days deviation. From there, a delay will be defined as a period of more than 24 days between 2 subsequent infusions (from the second infusion). The number of days delay will be calculated as follows:

$$[\text{date of infusion (i)} - \text{date of infusion (i-1)}] - 24 \text{ days, where } i=2,3,..I$$

If the value above is >0 days, then this will be classed as a delay. A subject may have more than one treatment delay throughout the course of treatment.

The summary of carboplatin treatment exposure and compliance table will include the following information:

- Duration of carboplatin therapy (weeks): summary statistics.
- Number of initiated cycles for carboplatin: summary statistics
- Total number of carboplatin infusions received: number of subjects with infusions: 0, 1, 2, 3, 4, 5, 6, others, missing
- Cumulative actual treatment dose of carboplatin (mg): summary statistics.
- Dose intensity of carboplatin (mg/ 3 weeks) overall and by cycle: summary statistics.
- Relative dose intensity of carboplatin (%): < 60%, 60% - < 80%, 80% - < 90%, 90% - 110%, > 110%.

- Number of subjects with delayed carboplatin infusions, and maximum length of delay (no delay including 1-2 days delay, 3-8 days, 9-15 days,  $\geq 16$  days)

An additional table will provide the following statistics:

- Overall duration of cisplatin and carboplatin treatment (weeks) defined as:

$$\text{overall duration} = \left( \frac{(\text{date of last dose} - \text{date of first dose}) + 21}{7} \right)$$

where date of last dose is the latest date between last dose of cisplatin and last dose of carboplatin, and date of first dose is the first dosing date of cisplatin.

- Overall number of cycles from the date of first dose of cisplatin until the latest date between last dose of cisplatin and last dose of carboplatin
- Number of subjects with cisplatin treatment by cycle
- Number of subjects with carboplatin treatment by cycle

In addition, a listing will provide detail on carboplatin exposure for each subject based on “Carboplatin administration” eCRF page.

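### SAP 15.3 computes the planned carboplatin dose by one formula for everyone, so relative dose intensity has the wrong denominator for subjects dosed by the protocol's other permitted formula

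*SAP*

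**What the plan says.** Protocol 6.4.1.1.2 has the carboplatin dose calculated from renal function "using the Calvert formula or the Chatelut formula, given that the target AUC is 5". It does not write out either formula. Protocol 8.5.4 lists among the exposure measures "relative dose intensity (actual dose given/planned dose").

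SAP 15.3 takes the actual dose from the eCRF but recalculates the planned dose: "The planned dose (mg/3weeks) of carboplatin at each cycle is defined based on the Area under curve (AUC) = 5" and on the "Glomerular filtration rate (GFR) as collected on the “Carboplatin administration” eCRF page". The equation given is AUC × (GFR + 25), and there is no alternative for subjects dosed another way. RDI is then "the dose intensity of carboplatin divided by the mean of planned doses at each cycle". The reporting bands are: "Relative dose intensity of carboplatin (%): < 60%, 60% - < 80%, 80% - < 90%, 90% - 110%, > 110"%.

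The dose-reduction table in SAP 15.1 gives minimum doses per subject "clustered according to the proportions of the planned dose". Its carboplatin column shows AUC 5 in the 100% row and, for the lower categories, "Based on planned dose given in the CRF". SAP Section 9 declares no changes from the protocol's planned analyses.

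**The concern.** RDI is meant to show how much of the intended dose a subject received. If the intended dose came from one permitted formula and the denominator comes from the other, the ratio mixes compliance with the difference between the formulas. A subject who received every planned milligram on time could then fall outside the 90–110% band. In the opposite direction, a real reduction could be partly masked.

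SAP 15.1 points to the CRF planned dose for the same drug, so the SAP does not hold to one definition of planned dose. At stake is whether the carboplatin exposure table can be read as compliance for these subjects. No efficacy result depends on it.

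**Working it through.** The documents state no numerical result on this point, so there is no plan figure to reproduce. The check applies the SAP 15.3 formulas directly.

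**Inputs from the documents**
- Duration in weeks = (last dose date − first dose date + 21) / 7 (SAP 15.3).
- Dose intensity = cumulative dose / (duration / 3) (SAP 15.3).
- Planned dose = 5 × (GFR + 25) (SAP 15.3).
- RDI = 100 × dose intensity / mean planned dose (SAP 15.3).
- One reduction step, AUC 5 to AUC 4, i.e. 20% (Protocol Table 6.5).
- Creatinine clearance at entry of at least 60 mL/min (Protocol 5.3.1), used as the lowest illustrative GFR.

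**Assumed input.** r = (dose by the other permitted formula) / (dose by the SAP equation), same subject, both at AUC 5. The documents give no value; the range tried is 0.70 to 1.30.

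**Self-check.** Take four on-time cycles (days 0, 21, 42, 63) and GFR 80.
- Duration = (63 + 21) / 7 = 12 weeks, so dose intensity = cumulative dose / 4.
- Planned dose = 5 × 105 = 525 mg.
- Dosed by the SAP equation at AUC 5: 4 × 525 / 4 = 525 mg, RDI 100%.
- At AUC 4 throughout: 4 × 105 = 420 mg per cycle, RDI = 420 / 525 = 80%, matching the protocol's 20% step.
- GFR 60, 100 and 120 (planned 425, 625 and 725 mg) give the same 100% and 80%.

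**Full, on-time AUC 5 dosing by the other formula (GFR 80).** Each dose is r × 525 mg, so RDI = 100 × r.

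| r | Dose (mg) | RDI by SAP 15.3 | Band |
|---|---|---|---|
| 0.70 | 367.5 | 70% | 60–<80% |
| 0.80 | 420 | 80% | 80–<90% |
| 0.90 | 472.5 | 90% | 90–110% |
| 1.00 | 525 | 100% | 90–110% |
| 1.10 | 577.5 | 110% | 90–110% |
| 1.20 | 630 | 120% | >110% |
| 1.30 | 682.5 | 130% | >110% |

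The band changes only for r below 0.90 or above 1.10. At r = 0.80 the subject cannot be told apart, on RDI, from one reduced to AUC 4 under the SAP equation.

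**Gap needed to leave the band.** This is just over 10% of the planned dose: 42.5 mg at GFR 60, 52.5 mg at 80, 62.5 mg at 100 and 72.5 mg at 120. In clearance terms, 0.1 × (GFR + 25) is 8.5, 10.5, 12.5 and 14.5 mL/min.

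**Alternative denominators.** With the AUC 5 dose by the formula actually used, RDI is 100% for full dosing at any r, and 80% for AUC 4 throughout. With a CRF planned dose rewritten after a reduction, AUC 4 throughout would show 100%, which hides the reduction. The denominator therefore has to be the unreduced dose.

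**The case against.** The strongest defence is that a common reference dose is deliberate. For the other drugs the SAP divides by a fixed protocol dose (250 mg/m²/week for cetuximab, 75 mg/m² per cycle for cisplatin, 750 × 5 mg/m² per cycle for 5-FU), and one AUC 5 calculation from the recorded GFR looks like the carboplatin counterpart. This does not remove the problem. Those fixed doses are the protocol's own reference for every subject, whereas the protocol's reference for carboplatin is AUC 5 by either formula.

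Other objections stand and limit the point:
- The documents neither write out the second formula nor compare the two. The size, direction and frequency of any discrepancy cannot be derived from them.
- The two planned-dose definitions need not give two conflicting printed results. The minimum-relative-dose summary is listed for cetuximab, cisplatin and 5-FU but not for carboplatin, and the 100% row of the SAP 15.1 table also shows AUC 5.
- The exposure output also includes cumulative dose in mg, dose intensity in mg per 3 weeks and a subject listing, so the underlying data remain visible.

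**Conclusion.** The planned-dose rule in SAP 15.3 is wrong for any subject dosed by a permitted formula other than AUC × (GFR + 25), and the SAP's two planned-dose definitions differ. This is a minor point. It affects only subjects switched to carboplatin and dosed by the other formula, and it changes only a descriptive exposure summary. The identity RDI = 100 × r assumes full, on-time dosing; r itself is unknown.

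Three stronger readings are tempting, and the documents support none of them.
- A reader might infer that fully dosed subjects will be reported as under- or overdosed. That needs r outside 0.90–1.10, which is not shown. The RDI bands also carry no such labels: overdose is handled separately in Protocol 6.12 and SAP Appendix 1.
- A reader might put a count on it, for example 16 subjects if 20% of 240 switch and one third use the other formula (0.20 × 240 / 3). Neither share is in the documents, and the number may be zero.
- A reader might infer that the same subject will appear with contradictory results in two tables. The difference lies in the definitions; the listed carboplatin outputs do not include the second measure.

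**What to change.** Use one planned-dose definition for carboplatin in SAP 15.1 and 15.3: the unreduced AUC 5 dose by the formula the site used for that subject. If the formula was not recorded, use the CRF planned dose before any dose reduction. A reduction to AUC 4 throughout then still shows as 80%. This concerns the exposure calculation only and takes no position on which dosing formula sites should use.

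The cost is a short SAP wording change and its programming, provided the CRF identifies the formula or keeps the unreduced planned dose. The documents do not show that it does either: they show a GFR field on the carboplatin page and a planned dose in the CRF. If neither item is available, keep the current equation and footnote the RDI table to say that it assumes AUC × (GFR + 25) for all subjects.
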